5.2. Study Drug(s)

5.2.1. Description

The investigational medicinal products (IMP) for this study are edoxaban (DU-176b) and SOC anticoagulants (LMWH, SP Xa inhibitor and VKA).

Edoxaban will be supplied as a one month treatment interval as tablets (15 and/or 30 mg strength) or granules for oral suspension 60 mg. Subjects will be instructed to take edoxaban (tablets or granules) orally once a day, at the same time every day, with or without food. Tablets should be swallowed with a glass of water.

- 60 mg dose will be dispensed with two 30 mg tablets
- 45 mg dose will be dispensed with one 30 mg tablet plus one 15 mg tablet
- 30 mg dose will be dispensed with one 30 mg tablet

The SOC drugs will be supplied as a one month treatment interval sourced locally by the Investigator or centrally by the Sponsor.

If local sourcing is used, the Investigator is allowed to utilize LMWH, VKA, or SP Xa inhibitors according to the site SOC treatment (no strength restrictions).

If central sourcing is used only enoxaparin as LMWH, fondaparinux as SP Xa inhibitor, and warfarin as VKA will be provided by the Sponsor at fixed doses.

The Sponsor will provide SOC treatment as follows:

- Enoxaparin (LMWH) will be provided to the subjects as solution for SC injection in pre-filled syringes with 60 mg/0.6 mL, 80 mg/0.8 mL, and 100 mg/1.0 mL concentration for injection, or as multiple dose vials (for subjects <10 kg) for injection where allowed per standard clinical practice. Guidance on dosing and dispensing is provided in Appendix [17.2](#).
- Fondaparinux (SP Xa inhibitor) will be supplied as solution for SC injection in pre-filled syringes (2.5 mg/0.5 mL, 5.0 mg/0.4 mL, 7.5 mg/0.6 mL, 10.0 mg/0.8 mL and

where available 1.5 mg/0.3 mL). Guidance on dosing and dispensing is provided in Appendix 17.2.

- Warfarin (VKA) will be supplied as tablets (0.5 mg, 1.0 mg, and 3.0 mg). Various doses will be available for INR maintenance in the therapeutic range of ≥ 2.0 and ≤ 3.0 . Guidance on dosing and dispensing is provided in Appendix 17.2.

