5.2.4.2. Instruct the subject randomized to SOC treatment

Subjects randomized to SOC treatment arm will receive SOC anticoagulant according to the study site's SOC treatment as follows (alone or combination):

- LMWH (alone or followed with VKA)
- SP Xa inhibitors (alone or followed with VKA)
- Vitamin K antagonist (VKA)

If Investigators choose to use centrally sourced SOC treatment from Sponsor, the subject will be treated as follows:

- For subjects randomized to enoxaparin: for neonates or children receiving either once- or twice-daily therapeutic enoxaparin the drug should be monitored to a target anti-FXa level of 0.5 to 1.0 units/mL in a sample taken at 4 hours post-dose for therapeutic levels. Monthly monitoring of anti-FXa levels is recommended. More frequent anti-FXa levels can be recommended as per Investigator's decision.
- For subjects randomized to fondaparinux: dosing of 0.1 mg/kg/day (0.05 mg/kg/day for subjects with renal disease). Monitoring fondaparinux levels (0.5- 1 mg/L) can be recommended as per Investigator's decision.
- For subjects randomized to warfarin: the dose should be titrated to achieve a target INR of 2.5 (≥ 2.0 and ≤ 3.0). Visits will be at the discretion of the Investigator and captured as unscheduled visits for data collection. Adjustment of the maintenance dose of VKA will be dependent on INR monitoring as follows:
 - INR = 2.0 to 3.0, no change in dose
 - INR = 1.1 to 1.4, increase dose by 20%

- INR = 1.5 to 1.9, increase dose by 10%
- INR = 3.1 to 3.5, decrease dose by 10%
- INR >3.5, hold VKA until INR is <3.5, then decrease dose by 20% when restarted.

To initiate SOC post screening, it is recommended to test infants and children every 4 weeks once a stable dose of VKA has been achieved. However, depending on the site's clinical practice and PI's discretion, the subjects can be tested at the physician's discretion and/or according to local practice. More frequent INR testing is recommended in infants and children receiving VKA with any change in diet or medication or when an illness occurs. An unscheduled visit will need to be performed to document the discretionary INR measurement and potential VKA dosage change as an unscheduled visit day.

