- For subjects in whom clinicians prescribe warfarin, this will be started on Day 1. Heparin (exoxaparin or fondaparinux or UFH depending on the therapy received during pre-randomization period) will be discontinued when INR ≥ 2.0 and ≤ 3.0 for 2 consecutive measurements obtained at least 24 to 48 hours apart. The subject will continue warfarin for the remainder of the study treatment period.

The Investigator will use discretion to decide when and how often to repeat INR or anti-FXa levels or aPTT measurements or fondaparinux levels. These measurements will be taken in the clinic, or alternatively, optional site-specific local laboratory (Appendix 17.2).

6.3.3. Monthly Visits (Months 1 and 2; Visits 3 and 4) for both arms:

Starting with the Month 1 visit, subjects will return to the clinic every 30 days \pm 5 days (depending on the visit, see Schedule of Events in Appendix 17.1) until the Month 3 visit (Visit 5) or study withdrawal. For Cohort 5, the subjects may return to the clinic earlier after the first month, depending on the duration of the therapy (at least 6 to 12 weeks) and imaging at 6 weeks for thrombus resolution.

During study drug interruptions and after study drug discontinuation, subjects will be followed for efficacy and safety endpoints and SAEs until the Month 3 visit (Visit 5) or earlier in Cohort 5 subjects (6-12 weeks). A 30 day Follow-Up Visit (Visit 9) for safety assessment is required after the Month 3 visit (for Cohort 5, the intended duration of treatment is 6 to 12 weeks).

At these monthly on-site visits, anti-FXa levels assessments and aPTT measurements will be performed for the subjects on SOC with LMWH or SP Xa inhibitor, fondaparinux levels if applicable, and INR assessments will be performed for the subject on SOC with VKA. Additional interim visits may be scheduled, at the Investigator's discretion, for anti-FXa levels/INR monitoring.

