9. SAFETY EVALUATION AND REPORTING

9.1. Adverse Event Collection and Reporting

In the event of a Medical Emergency, the Investigator at the study site will institute any medical procedures deemed appropriate. A 24-hour Urgent Medical Contact will be provided to contact the Medical Monitor for further guidance.

Sites will receive a contact card where the following numbers (24-hour Urgent Medical Contact) are provided:

PPD [REDACTED] (primary number)

PPD [REDACTED] (alternative number)

The medical call center will contact Medical Monitor for the assigned region.

All AEs (see Section 9.4.1 for definitions) occurring after the subject signs the Informed Consent Form and up to 30 days after the last dose of study drug (ie, the Follow-Up Visit), whether observed by the Investigator or reported by the subject, will be recorded on the Adverse Event CRF page. Medical conditions (including laboratory values/vital signs that are out of range) that were diagnosed or known to exist prior to Informed Consent will be recorded as part of medical history.

All AEs, serious adverse events (SAEs), bleeding, and events of special interest are to be reported according to the procedures in Section 9.5.

All laboratory results and vital signs should be appraised by the Investigator to determine their clinical significance. Isolated abnormal laboratory results or vital sign findings should be reported as AEs if they are symptomatic, lead to study drug discontinuation, dose reduction, require corrective treatment, or constitute an AE in the Investigator's clinical judgment.

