9.4. Adverse Event

9.4.1. Definition of Adverse Event

An adverse event is any untoward medical occurrence in a subject administered a pharmaceutical product and that does not necessarily have to have a causal relationship with this treatment. An AE can therefore be any unfavorable and unintended sign (including an abnormal laboratory finding, for example), symptom, or disease temporally associated with the use of a medicinal product, whether or not considered related to the medicinal product (ICH E2A Guideline. Clinical Safety Data Management: Definitions and Standards for Expedited Reporting, Oct 1994).

It is the responsibility of Investigators, based on their knowledge and experience, to determine those circumstances or abnormal laboratory findings which should be considered adverse events.

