11.4.3.2. Adverse Event Analyses

Adverse events will be coded according to the Medical Dictionary for Regulatory Activities (MedDRA).

Treatment-emergent AEs (TEAEs) are defined as AEs that occur, having been absent before the initial of study treatment, or worsen in severity after the initiation of study treatment administration. Adverse events that start or worsen after the 30th day following the calendar date of the dose of the last study drug are defined as post-treatment AEs.

The incidence of TEAEs will be presented for the Safety Analysis Set for the on treatment period and from the date of the first dose of study drug to the date of the last dose of study drug, respectively, by System Organ Class, by preferred term, and by treatment arm. TEAEs will be

further summarized by relationship to the study drug, and by severity. Frequent TEAEs (reported by $\geq 5\%$ of subjects in any treatment arm) will also be summarized by treatment arm for the on-treatment period and from the date of the first dose of study drug to the date of the last dose of study drug, respectively. The incidence of death, SAEs, drug-related SAEs, and AEs leading to discontinuation of study drug will also be summarized. All AEs will be included in a data listing and a listing to display the coding of AEs will be prepared as well.

Similarly, the number and percentage of deaths, subjects reporting treatment-emergent SAEs, and TEAEs leading to discontinuation of study treatments will be tabulated.

A by-subject AE (including treatment-emergent) data listing including but not limited to verbatim term, preferred term, system organ class, preferred term, and relationship to study drug will be provided. Deaths, other SAEs, and other significant AEs, including those leading to discontinuation of study drug, will be listed.

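### Section 9.1 does not exempt anticoagulation-monitoring values, so routine downward titration of standard-of-care drugs can be counted as adverse events in that arm

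*Combined protocol and SAP*

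**What the plan says.** **The reporting rule.** Section 9.1 first asks for clinical appraisal: "All laboratory results and vital signs should be appraised by the Investigator to determine their clinical significance". It then gives the rule: "Isolated abnormal laboratory results or vital sign findings should be reported as AEs if they are symptomatic, lead to study drug discontinuation, dose reduction". The list goes on to results that need corrective treatment or that the Investigator judges to be AEs, and the items are joined by *or*. Section 9.4.1 leaves it to Investigators "to determine those circumstances or abnormal laboratory findings which should be considered adverse events".

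**What counts as study drug.** Section 5.2.1: "The investigational medicinal products (IMP) for this study are edoxaban (DU-176b) and SOC anticoagulants (LMWH, SP Xa inhibitor and VKA").

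**Titration in the SOC arm.** For centrally sourced warfarin, Section 5.2.4.2 has "INR = 3.1 to 3.5, decrease dose by 10" (per cent) and "INR >3.5, hold VKA until INR is <3.5, then decrease dose by 20% when restarted". Table 17.4 lowers the fondaparinux dose at levels above 1 mg/L. At the monthly visits of Section 6.3.3, "INR assessments will be performed for the subject on SOC with VKA", with extra checks at discretion. Note f to Table 17.1 describes monthly INR assessment for adjusting VKA dose, without limiting it to centrally supplied drug.

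**Dose reduction in the edoxaban arm.** Section 5.3.1 lists four reasons: eGFR at 30-50% of normal, a P-gp inhibitor, low weight for age, and age of 28 days or less. None is an INR or a drug level.

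**The tables.** Section 11.4.3.2 summarises TEAEs by arm. They are "further summarized by relationship to the study drug, and by severity", and those reported by at least 5% of subjects in either arm are shown again as frequent TEAEs.

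**The concern.** An INR slightly above range on warfarin, followed by a small planned decrease, is ordinary management of that drug. Under the dose-reduction trigger it becomes an AE without symptoms, bleeding or other treatment. Section 9.4.4 then makes a related classification likely, because one route to it is a plausible time sequence plus an effect predicted by the drug's known pharmacology.

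Edoxaban subjects cannot produce this type of AE. Some have PT, aPTT and anti-FXa measured at Day 5, but no individual dose rule follows from those values. In an open-label trial, part of any SOC excess in the overall, related or frequent TEAE tables could then reflect how the comparator is dosed and not a difference in harm. Sites that apply the trigger literally would also report differently from sites that rely on Investigator judgment.

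**Working it through.** The documents state no figure for this effect, so there is none to reproduce. The check has two parts.

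**1. Does the text produce the effect?**

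| Step | SOC arm | Edoxaban arm |
|---|---|---|
| Is it study drug? | Yes (5.2.1) | Yes (5.2.1) |
| Reduction on INR? | Warfarin: 5.2.4.2 and Table 17.3 | None (5.3.1) |
| Reduction on drug level? | Fondaparinux: Table 17.4. Enoxaparin has an anti-FXa target but no reduction table | None (5.3.1) |
| Reduction on another laboratory value? | Lower fondaparinux dose in renal disease (5.1.1.2) | Confirmed eGFR 30-50% of normal (Synopsis, Table 5.1 notes, 5.3.1); creatinine at Months 1, 3, 6, 9 and 12 (9.8.2) |
| Monitoring values exempt from the AE rule? | Not in the protocol | Not in the protocol |

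So the effect exists on a literal reading, but only for INR and drug-level titration, and only for decreases or stops. Upward titration is not a trigger.

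**2. How large could it be?** The documents give no SOC drug mix, no out-of-range rate and no background TEAE rate. All inputs below are assumptions, except the 137 subjects per arm (Section 11.6).

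Let *s* be the share of SOC subjects on a drug with a laboratory-driven reduction, *p* the chance of at least one such reduction, and *b* the background TEAE incidence, equal in both arms and independent of titration.

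- SOC subjects with at least one titration AE = 137 × *s* × *p*
- Rise in SOC any-TEAE incidence = (1 − *b*) × *s* × *p*

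| Case | *b* | *s* | *p* | Subjects of 137 | Rise in any-TEAE incidence |
|---|---|---|---|---|---|
| Low | 0.9 | 0.2 | 0.2 | 137 × 0.04 = 5.5 | 0.1 × 0.04 = 0.4 points |
| Middle | 0.7 | 0.5 | 0.5 | 137 × 0.25 = 34.2 | 0.3 × 0.25 = 7.5 points |
| High | 0.5 | 0.8 | 0.8 | 137 × 0.64 = 87.7 | 0.5 × 0.64 = 32 points |

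On the edoxaban side, an assumed 0 to 10% with a confirmed eGFR reduction gives 0 to 13.7 subjects of 137 with an AE under the same rule. With *e* for that share, the net SOC excess is (1 − *b*)(*sp* − *e*). At *sp* = 0.04, *e* = 0.10 and *b* = 0.9 it is 0.1 × (−0.06) = −0.6 points. The sign is therefore not fixed by the text.

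**Frequent-TEAE threshold (5%).** This applies to a single term such as raised INR, so background TEAEs dilute it less. With VKA share *v*, chance *r* that a check is above range, and *k* independent checks, the share with the term is *v*(1 − (1 − *r*)^*k*):

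- *v* = 0.2, *r* = 0.1, *k* = 3: 0.2 × 0.271 = 5.4% (7.4 subjects)
- *v* = 0.3, *r* = 0.2, *k* = 3: 0.3 × 0.488 = 14.6% (20 subjects)
- *v* = 0.5, *r* = 0.2, *k* = 6: 0.5 × 0.738 = 36.9% (50.5 subjects)
- *v* = 0.1, *r* = 0.1, *k* = 3: 0.1 × 0.271 = 2.7% (3.7 subjects)
- *v* = 0.2, *r* = 0.05, *k* = 3: 0.2 × 0.143 = 2.9% (3.9 subjects)

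Whether the term passes 5% depends on the inputs chosen.

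**The case against.** **Investigators filter these values.** Appraisal comes first, the rule covers isolated abnormal results, and Section 9.4.1 leaves the decision to the Investigator. Nothing says that an expected INR of 3.1 on warfarin is abnormal or untoward. This stands in part: a reader might infer that any out-of-range value must be reported, and the text does not go that far. But judgment is one trigger among several and does not override dose reduction. If it is read as an override, reporting varies by site. Either reading leaves the question open.

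**The titration rules do not bind the whole arm.** The Section 5.2.4.2 list applies when the sponsor supplies the drug, Tables 17.3 and 17.4 are guideline recommendations, and fondaparinux monitoring is discretionary. Local SOC follows the site's own regimen. This stands, and it makes the effect depend on site and drug. Local VKA is nevertheless INR-adjusted.

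**VKA use may be low.** Section 1.2 notes that tablets are difficult for young children, and Section 1.1 that many children stay on LMWH. This stands, and it favours the lower end of the range.

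**Edoxaban has its own trigger.** A reader might infer that the AE comparison favours edoxaban by construction. The eGFR rule shows that laboratory-driven reductions are not confined to SOC. It is not an equivalent offset, since it needs a confirmed change in organ function, but its size is unknown.

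**Nothing confirmatory depends on it.** TEAEs are summarised without a test. The formal safety comparison is a Cox analysis of major and CRNM bleeding (Section 11.4.3.1), adjudicated blind (Section 9.2.1). The CRNM definition mentions a change in antithrombotic therapy, but only in response to an overt bleed, so titration alone does not qualify. This stands in full. A raised-INR term would also be visible in its own row, although the overall and related totals would still contain it.

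**Other documents may settle it.** Section 11.7 defers analysis definitions to the SAP, and Section 12.2 refers to data-entry guidelines. An exemption there cannot be excluded from the text available.

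**Conclusion.** The point holds in limited form. Section 9.1 leaves unsettled whether monitoring values that lead only to planned titration are AEs. Read literally, it can inflate TEAE and related-TEAE counts in the SOC arm, and reporting may differ by site. The asymmetry concerns INR and drug-level titration only.

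The documents do not fix its size. The gross rise in SOC any-TEAE incidence runs from 0.4 to 32 percentage points for assumed *b* of 0.5 to 0.9 and *s* and *p* of 0.2 to 0.8. The edoxaban eGFR trigger reduces the net difference by an unknown amount.

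Two stronger inferences fail. A bias built into the AE comparison is not shown, because the net direction depends on inputs the documents do not give. Nor does a titration term necessarily reach the 5% frequent-TEAE threshold: modest inputs give 2.7% or 2.9%. The efficacy and adjudicated bleeding results are untouched. This is a worthwhile, inexpensive improvement to descriptive safety reporting.

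**What to change.** State in Section 9.1 and the eCRF guidelines that asymptomatic INR, anti-FXa, aPTT or fondaparinux values leading only to planned titration are recorded as anticoagulation-monitoring data and tabulated separately, not as AEs. The exemption should not apply if the value is symptomatic, serious, accompanied by bleeding or VTE, or needs other corrective treatment.

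For AEs already recorded, flag titration-only terms, preferably without knowledge of the results by arm, and present the overall, related and frequent TEAE tables with and without them.

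The cost is one reporting sentence, a data flag and one repeat of three sets of tables. No dosing or titration rule changes. The downside is small: asymptomatic over-anticoagulation moves from the AE tables to a monitoring table, which should therefore appear beside them in the study report.

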9.2. Safety Endpoint Event(s)

All potential safety endpoints will be adjudicated by an independent CEC. Study endpoints and safety data will be periodically reviewed by an IDMC to ensure the safety of study participants.

The safety related secondary objectives are:

- To compare edoxaban against SOC with regard to the combination of major and CRNM bleedings occurring during treatment or within 3 days of completing or interrupting or stopping study during the first 3-month treatment period (for Cohort 5, the intended duration of treatment is at least 6 to 12 weeks).
- To compare edoxaban against SOC with regard to all bleedings which occur from first to the last dose + 30 days.
- To compare edoxaban against SOC with regard to a composite combination of major and CRNM bleedings from first to the last dose + 30 days.

The corresponding safety endpoints are:

- A combination of major and CRNM bleedings occurring during treatment or within 3 days of completing or interrupting or stopping study during the first 3-month treatment period. For subjects in Cohort 5, ie,<6 months old, the primary safety endpoint, is a combination of major and CRNM bleedings occurring during treatment or within 3 days of completing or interrupting or stopping study within 6 to 12 weeks period + 3 days.
- All bleedings from first to the last dose + 30 days.
- A combination of major and CRNM bleedings from first to the last dose + 30 days

9.2.1. Bleeding

Bleeding is a protocol-specified endpoint and a known concern associated with anticoagulant therapy including edoxaban and VKAs (including warfarin). All bleeding events will be reported in the eCRF as either an AE or SAE depending upon the seriousness criteria along with completion of the bleeding event form. All bleeding events will be adjudicated by the CEC.

Bleeding definitions are based on presentations/discussions at the Perinatal and Paediatric Haemostasis Subcommittee meetings during the 56th-58th Scientific and Standardization Committee (SSC) Meeting of the ISTH.²¹

Major bleeding is defined as a composite (ie, any) of the following:

- Fatal bleeding; and/or
- Symptomatic bleeding in a critical area or organ, such as intracranial, intra-spinal, intraocular, retroperitoneal, intra-articular, pulmonary, or pericardial, or intramuscular with compartment syndrome; and/or
- Bleeding causing a decrease in hemoglobin level of 2 g/dL (1.24 mmol/L) or more, or leading to transfusion of the equivalent of two or more units of whole blood or red blood cells (RBCs).

Clinically relevant non-major bleeding is defined as either of the following:

- Acute or sub-acute clinically overt bleed that does not meet the criteria for a major bleed but prompts a clinical response, in that it leads to at least one of the following:
 - A hospital admission for bleeding;
 - A physician-guided medical or surgical treatment for bleeding or
 - A change in antithrombotic therapy (including interruption or discontinuation of study drug).

Minor bleeding is defined as follows:

- Any overt or macroscopic evidence of bleeding that does not fulfill the above criteria for either major bleeding or clinically relevant, non-major bleeding

Minimal criteria defining a significant bleeding per ISTH²⁷ are as follows:

For each specific bleeding symptom, the ISTH/Scientific and Standardization Committee (SSC) joint working group proposed minimal criteria in order to classify a symptom as significant:

1. Epistaxis:

- Any nosebleed, especially occurring after puberty that causes subject concern (eg, interference or distress with daily or social activities) is considered significant.
- In general, epistaxis should not be considered significant when it lasts less than 10 minutes, has a frequency of <5 episodes/year, has a seasonal occurrence, or is associated with infections of the upper respiratory tract or other identifiable cause (e.g., dusty dry air).

2. Cutaneous bleeding:

- Bruises are considered significant when 5 or more (>1 cm) in exposed areas;
- Petechiae are considered significant when adequately described by the subject or relatives;
- Hematomas are considered significant when occurring without trauma.

3. Minor cutaneous wound:

- Any bleeding episode caused by superficial cuts (eg, by shaving razor, knife, or scissors) or that requires frequent bandage changes is considered significant.
- Insignificant bleeding from wounds includes those of duration <10 minutes and lesions that usually require stitches in normal subjects (eg, under the chin).
- Symptoms should also be manifest on more than 1 occasion to be considered significant.

4. Oral cavity bleeding:

- Gum bleeding should be considered significant when it causes frankly bloody sputum and lasts for 10 minutes or longer on more than one occasion.
- Tooth eruption or spontaneous tooth loss bleeding should be considered significant when it requires assistance or supervision by a physician, or lasts at least 10 minutes (bleeding associated with tooth extraction is considered separately).
- Bleeding occurring after bites to lips, cheek, and tongue should be considered significant when it lasts at least 10 minutes or causes a swollen tongue or mouth.

5. Hematemesis, melena, and hematochezia:

- Any gastrointestinal bleeding that is not explained by the presence of a specific disease should be considered significant.

6. Hematuria:

- Only macroscopic hematuria (from red to pale-pink urine) that is not explained by the presence of a specific urologic disease should be considered significant.

7. Tooth extraction:

- Any bleeding occurring after leaving the dentist's office and requiring a new, unscheduled visit or prolonged bleeding at the dentist's office causing a delay in the procedure or discharge should be considered significant.

8. Surgical bleeding:

- Any bleeding judged by the surgeon to be abnormally prolonged, that causes a delay in discharge, or requires some supportive treatment is considered significant.

9. Menorrhagia:

- Any bleeding that interferes with daily activities such as work, housework, exercise or social activities during most menstrual periods should be considered significant.
- Criteria for significant bleeding may include any of the following: changing pads more frequently than every 2 hours; menstrual bleeding lasting 7 or more days; and the presence of clots >1 cm combined with a history of flooding.

10. Muscle hematomas or hemarthrosis.

- Any spontaneous joint/muscle bleeding (not related to traumatic injuries) is considered significant.

11. Central nervous system bleeding.

- Any subdural or intra-cerebral hemorrhage is considered significant

All safety and efficacy endpoints described will be adjudicated in a blinded manner by the CEC.

The CEC will require all available details about the bleeding event and related information to allow successful objective adjudication of the event. Details may include, but are not limited to, information such as the following:

- Location of the bleeding;
- Duration of the bleeding;
- Fatality
- Treatment for bleeding event, including notes or summary of the recommendations from a healthcare professional from whom medical treatment was obtained;
- Magnitude of the bleeding (including size if skin or subcutaneous hematoma);
- Hemoglobin levels at randomization and at the time of the bleeding event, lowest value, pre- and post-transfusion values, and after resolution of the bleeding event;
- Diagnostic tests done to evaluate the bleeding such as endoscopy (GI bleed), ENT consult (ear, nose, throat bleed), urology consult (hematuria or urogenital bleeding), surgical consult (skin and soft tissue, including intra-abdominal bleeding), gynecological consult (uterine or vaginal bleeding), neurological consult (intracranial bleed), or ophthalmology consult (intraocular bleed);
- Diagnostic scans (CT scans or MRIs), ultrasounds or x-rays performed to evaluate the bleeding (intracranial bleed)
- Any other information that can be of help to the CEC to allow successful objective adjudication of the bleeding event.

